8.3.9.2 Management of Hematologic Toxicity and Risk of Infections

Idasanutlin has exposure-dependent suppressive effects on bone marrow progenitors and thus a balance between the desired effects on PV progenitor cells and the normal cells must be targeted. At the dose levels used in this study, a significant reduction in the counts of normal blood cells is not expected to be observed. Specific guidelines to manage the risk of hematologic toxicity are provided in [Table 8](#).

Frequent monitoring of hematologic values (count of blood cells, including differential) is recommended. See [Table 8](#) for guidelines for the management of hematologic toxicity.

Increased hemorrhagic risk should be proactively managed following institutional guidelines in case of Grade ≥ 2 thrombocytopenic events.

In case of a patient showing ANC count $< 1.0 \times 10^9/L$ and concomitant fever, idasanutlin should be permanently discontinued, *unless AEs are clearly unrelated to the treatment*. Similarly, in case of a Grade ≥ 3 systemic infection associated with any grade leukopenia (refer to [Appendix 12](#) for the list of PT considered pertinent to leukopenia) idasanutlin should be permanently discontinued, *unless AEs are clearly unrelated to the treatment*.

Table 8 Guidelines for Managing Hematologic Toxicity

Hgb level	ANC / PLT level	Management

Hgb ≥12 g/dL (women), 13 g/dL (men) (>7.5mmol/L [women]; >8.1 mmol/L [men]) AND
	
PLT ≥120 ×10⁹/L AND ANC ≥1.5 ×10⁹/L
	
 No dose modifications required.
	
PLT 75 to <120 ×10⁹/L AND ANC ≥1.5x10⁹/L
	
 Interrupt dose until PLT ≥120 ×10⁹/L. Resume with reduced idasanutlin dose with a 50-mg dose reduction (lowest idasanutlin dose is 100 mg; no dose modification required, if dose is already at 100 mg). If the event does not resolve within 28 days, discontinue treatment. ^a Monitor labs at least every 2 weeks until PLT ≥120 ×10⁹/L.
	
PLT 50 to <75 ×10⁹/L AND/OR ANC 0.5 to <1.5 ×10⁹/L
	
 Interrupt dose until PLT ≥120 ×10⁹/L and ANC ≥1.5 ×10⁹/L. Resume with reduced idasanutlin dose with a 50-mg dose reduction (lowest idasanutlin dose is 100 mg). If the event does not resolve within 28 days despite dose interruption, discontinue treatment. No further treatment if recurrence at 100 mg (discontinue patient). Monitor labs at least every week until PLT ≥120 ×10⁹/L or ANC ≥1.5 ×10⁹/L.
	
PLT <50 ×10⁹/L OR ANC <0.5 ×10⁹/L OR ANC <1 ×10⁹/L and any episode of fever (38°C)
	
 No further treatment (discontinue patient).

Hgb 8 to <12 g/dL (women), 8 to <13 g/dL (men) (4.9 to <7.5 mmol/L [women]; 4.9 to <8.1 mmol/L [men]) AND
	
PLT ≥120 ×10⁹/L AND ANC ≥1.5 ×10⁹/L
	
 Interrupt dose until Hgb ≥12g/dL (women), 13 g/dL (men). First episode: Resume without dose modifications. If recurrent, resume with reduced idasanutlin dose with a 50-mg dose reduction (lowest idasanutlin dose is 100 mg; no dose modification required, if dose is already at 100 mg). If the event does not resolve within 28 days, discontinue treatment. ^a If recurrence more than twice on lowest dose (100 mg) of

Hgb level	ANC / PLT level	Management
		
idasanutlin, discontinue treatment. ^a
 
 • Monitor the labs at least every 2 weeks until and Hgb ≥ 12 g/dL (women), 13 g/dL (men).
	PLT 75 to $<120 \times 10^9/L$ AND ANC $\geq 1.5 \times 10^9/L$	
 • Interrupt dose until PLT $\geq 120 \times 10^9/L$ and Hgb ≥ 12 g/dL (women), 13 g/dL (men). • Resume with reduced idasanutlin dose with a 50-mg dose reduction (lowest idasanutlin dose is 100 mg; no dose modification required, if dose is already at 100 mg). • If the event does not resolve within 28 days or if recurrent, discontinue treatment. • Monitor labs at least every 2 weeks until PLT $\geq 120 \times 10^9/L$ and Hgb ≥ 12 g/dL (women), 13 g/dL (men).
	PLT 50 to $<75 \times 10^9/L$ AND/OR ANC 0.5 to $<1.5 \times 10^9/L$ OR	
 • Interrupt dose until ANC $\geq 1.5 \times 10^9/L$ and Hgb ≥ 12 g/dL (women), 13 g/dL (men) and PLT $\geq 120 \times 10^9/L$. • Idasanutlin may be resumed with a 50-mg dose reduction (lowest idasanutlin dose is 100 mg). • If the event does not resolve within 28 days or if recurrent, discontinue treatment. • Monitor labs at least every week until PLT $\geq 120 \times 10^9/L$ or ANC $\geq 1.5 \times 10^9/L$ or Hgb ≥ 12 g/dL (women), 13 g/dL (men).
	PLT $<50 \times 10^9/L$ OR ANC $<0.5 \times 10^9/L$ OR ANC $<1 \times 10^9/L$ and any episode of fever ($38^\circ C$)	
 • No further treatment. • Discontinue patient.
Hgb < 8g/dL (4.9 mmol/L) OR	ANC $<1 \times 10^9/L$ and any episode of fever ($38^\circ C$) OR ANC $<0.5 \times 10^9/L$ OR PLT $<50 \times 10^9/L$	
 • No further treatment. • Discontinue patient.

ANC = absolute neutrophil count; Hgb = hemoglobin; PLT = platelet.

^a The decision to extend the dose delay or to continue treatment will be made on the basis of the investigator's assessment of ongoing clinical benefit and in consultation with the Medical Monitor.

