The observation that treatment with 5 days of idasanutlin at doses lower than the MTD identified in solid tumor patients is able to control Hct levels in PV patients suggests that inhibition of the MDM2-p53 interaction may be an important pathway in treatment of this disease. New mechanisms such as MDM2 inhibition may affect the underlying PV biology in a positive manner, where current standard of care options have not been shown to do so in the majority of the patients.

The majority of the adverse events (AEs) recorded for idasanutlin treatment are transient in nature and reversible. Clinical experience to date suggests a dose-relationship for idasanutlin and GI AEs, with increased incidence of nausea, vomiting, and diarrhea at higher dose levels. Prophylaxis with anti-emetics is therefore *mandatory* for patients in this study. Cytopenias, manifesting as thrombocytopenia and neutropenia, are expected to occur at higher dose/exposure levels and appears to be related to toxicity on normal (non-PV) early hematopoietic progenitors. Frequent monitoring of hematologic values (count of blood cells, including differential) is required. The doses planned to be administered in this study are lower than the MTD in solid tumor patients.

Based on the non-clinical and clinical evidence supporting a potential clinical benefit of MDM2 inhibition in PV, the unmet medical need, and the observed safety profile of MDM2 inhibition to date, further clinical development of idasanutlin in this patient population is supported.

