8.3.4 Follow-Up of Adverse Events and Serious Adverse Events

8.3.4.1 Investigator Follow-Up

The Investigator should follow each AE until the event has resolved to baseline grade or better, the event is assessed as stable by the Investigator, the event is otherwise explained, the patient is lost to follow-up, or the patient withdraws consent. Every effort should be made to follow all SAE considered to be related to study treatment or trial-related procedures until a final outcome can be reported.

During the study period, resolution of AE (with dates) should be documented on the AE eCRF and in the patient's medical record to facilitate source data verification. If, after follow-up, return to baseline status or stabilization cannot be established, an explanation should be recorded on the AE eCRF.

All pregnancies reported during the study should be followed until pregnancy outcome and reported according to the instructions provided in Section 8.3.6.

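### In two Table 8 rows the weekly lab minimum ends when any one count recovers, although dosing stays on hold until all have; *or* should read *and*

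*Protocol*

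**What the plan says.** Table 8 sorts patients by hemoglobin and then by platelets (PLT) and neutrophils (ANC), both in ×10⁹/L. Two rows share the same PLT/ANC band, PLT 50 to <75 and/or ANC 0.5 to <1.5.

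- **Normal hemoglobin.** The hold rule is "Interrupt dose until PLT ≥120 ×10⁹/L and ANC ≥1.5 ×10⁹/L". The monitoring rule is "Monitor labs at least every week until PLT ≥120 ×10⁹/L or ANC ≥1.5 ×10⁹/L". The time limit is "If the event does not resolve within 28 days despite dose interruption, discontinue treatment", without the footnote that allows the delay to be extended.
- **Hemoglobin 8 to <12 g/dL (women) or 8 to <13 g/dL (men).** The hold lasts until ANC, hemoglobin and PLT have all recovered; the three are joined by *and* ("g/dL (women), 13 g/dL (men) and PLT"). The monitoring bullet opens "Monitor labs at least every week until PLT" and then joins the PLT, ANC and hemoglobin thresholds by *or*. The same 28-day limit applies, again without the footnote.

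The closest milder row (low hemoglobin, PLT 75 to <120, ANC at least 1.5) opens its monitoring bullet with "Monitor labs at least every 2 weeks until PLT" and joins PLT and hemoglobin by *and*, exactly as its hold rule does.

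Elsewhere, Section 2.3 states: "Frequent monitoring of hematologic values (count of blood cells, including differential) is required". It gives no interval, and Section 8.3.9.2 itself only recommends frequent monitoring. Section 8.3.4.1 adds: "The Investigator should follow each AE until the event has resolved to baseline grade or better".

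**The concern.** The hold and the monitoring that supports it should end on the same condition. Here the hold ends when all counts have recovered and the weekly minimum ends when one has. Because entry is by and/or, a patient with only one of PLT and ANC low has the other already above its threshold. Read literally, the weekly requirement has then lapsed on the day the hold begins.

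These rows contain the lowest PLT and ANC bands from which a patient may still be re-treated; the next band down (PLT <50 or ANC <0.5) means permanent discontinuation. They also carry a 28-day limit for resolution. A fixed weekly count shows further decline early and documents recovery in time against that limit. The table plainly intends closer monitoring here, since it moves from every 2 weeks in the milder rows to every week.

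**Working it through.** The plan gives no figure to reproduce. The check compares the two stopping conditions over every combination of counts that enters the rows.

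**Inputs (Table 8).**
- Entry: PLT 50 to <75 or ANC 0.5 to <1.5 or both, at each of two hemoglobin levels.
- End of hold: PLT ≥120 and ANC ≥1.5, plus hemoglobin recovered in the low-hemoglobin row.
- End of weekly labs: PLT ≥120 or ANC ≥1.5, or hemoglobin recovered in the low-hemoglobin row.

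**Step 1: entry combinations.** Cross PLT {50 to <75, 75 to <120, ≥120} with ANC {0.5 to <1.5, ≥1.5} and keep those that meet the entry condition. Four remain at each hemoglobin level:

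| PLT | ANC | Weekly-lab stop met at entry | End of hold met at entry |
|---|---|---|---|
| 50 to <75 | 0.5 to <1.5 | no | no |
| 50 to <75 | ≥1.5 | **yes** | no |
| 75 to <120 | 0.5 to <1.5 | no | no |
| ≥120 | 0.5 to <1.5 | **yes** | no |

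The results are the same at both hemoglobin levels, because in the low-hemoglobin row hemoglobin is below its threshold at entry and cannot trigger the stop. In total, 2 × 2 = 4 of 2 × 4 = 8 combinations already meet the weekly-lab stop, and 0 of 8 meet the end of hold. In the other 4, weekly labs end at the first count to recover.

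**Step 2: states during the hold.** Treat each count as recovered or not. With two counts there are 2² = 4 states; the *or* condition is met and the *and* condition is not in 2. With three counts there are 2³ = 8 states, and the two conditions differ in 6 (all except none recovered and all recovered). With *and* in the monitoring bullet both numbers fall to 0.

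**Step 3: does another row fill the gap?** The 4 affected combinations belong to these rows and to no milder one, so the every-2-weeks rule does not cover them. It starts to apply only once ANC is at least 1.5 and PLT has risen to at least 75.

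**Step 4: the interval lost.** Over the 28-day limit, weekly labs give 28/7 = 4 checks (days 7, 14, 21, 28). The milder low-hemoglobin row guarantees 28/14 = 2 (days 14 and 28). In the 4 affected combinations Table 8 guarantees none at a fixed interval. For example, PLT 100 with hemoglobin 11 g/dL has 2 guaranteed checks; PLT 60, ANC 2.0 and hemoglobin 11 g/dL has none.

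**The case against.** The best defense is that *or* mirrors the and/or of the entry condition and means whichever count was low. An instruction to monitor until a count recovers presupposes that it is below threshold, and a clinician is unlikely to read the bullet as cancelling itself. This is a reasonable guess at what the authors meant for a single low count. But the table does not say it, it leaves open what happens when both PLT and ANC are low, and it fails in the low-hemoglobin row. Hemoglobin is always low there, so at least two counts are below threshold and *or* cannot pick out one.

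The second line is that other duties fill the gap. Ending the hold and applying the 28-day rule both need blood counts. Section 1.3 requires acceptable labs before dosing. A lab result that interrupts treatment is an adverse event (Appendix 11, item 4) and is followed under Section 8.3.4.1. Section 8.2.4 requires unexplained significant abnormalities to be repeated. As far as the schedule can be read, Cycles 1 to 3 also have mid-cycle hematology. All of this stands and narrows the gap, but none of it sets a weekly interval during a hold, and Section 8.3.4.1 lets follow-up end once the event is judged stable.

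Three smaller points are also fair. Of the three milder hold rows, two depend on a single count, so only one is an informative comparison. The milder low-hemoglobin row with PLT 75 to <120 also lacks the footnote on extending the delay. And 4 of 8 counts combinations, not patients; the documents give no frequencies.

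**Conclusion.** The concern holds. In both rows the weekly-lab minimum can end while dosing is still on hold. In 4 of 8 entry combinations it has ended, on the literal text, before the hold begins, and the documents offer no reason for the difference from the hold rule.

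The consequence is limited to the mandated interval. Re-dosing still requires all counts to recover, so no unsafe re-dosing follows. Wrongful discontinuation is not shown, and the sample size and efficacy analysis are untouched. The conclusion rests on reading *or* as written, and on taking the stray *OR* at the end of the low-hemoglobin entry cell as adding no further entry condition. It is a wording error in an operative safety rule and worth correcting.

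**What to change.** In the weekly-monitoring bullet of both rows, replace *or* with *and*, so that weekly labs continue until the condition that ends the hold:

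- normal-hemoglobin row: PLT ≥120 and ANC ≥1.5 ×10⁹/L;
- low-hemoglobin row: the same, plus hemoglobin ≥12 g/dL (women) or ≥13 g/dL (men).

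This changes one word in the first cell and two in the second. The practical cost is a few extra blood counts in affected patients, at most 4 per 28-day hold.

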8.3.9.3 Management of Other Toxicities

Oral administration of idasanutlin was associated with body weight loss and/or reduced body weight gain associated with decreased food consumption in preclinical safety toxicology studies performed in cynomolgus monkeys. Decreased appetite and anorexia have been commonly reported during idasanutlin clinical development. It is recommended to investigators to monitor weight and intervene with nutritional support if required.

Fatigue and asthenia are common clinical signs associated with PV. During clinical development of idasanutlin, fatigue and asthenia were commonly observed and can be interrelated with GI toxicity and decreased appetite/anorexia. It is recommended to investigators to monitor root cause and intervene on underlying causes with nutritional support as clinically required.

Idasanutlin has hepatic toxicity as a potential risk. Accordingly, ALT, AST and bilirubin will be monitored throughout the trial as specified in Section 1.2 and will be captured as AESI as specified in Section 8.3.6. Patients at screening also need to have adequate hepatic function as described in the inclusion criteria (Section 5.1). Patients with active hepatitis will not be eligible for treatment as per Exclusion Criteria (Section 5.2). In the case of abnormal liver function test during the trial, patients will be managed as described in Table 6.

In previous clinical studies, electrolyte disorders (reported with the following PTs: hypercalcaemia, hyperkalaemia, hypernatraemia, hypocalcaemia, hypokalaemia, hypomagnesaemia, hyponatremia, hyperphosphataemia, hypophosphataemia) very commonly occurred in patients treated with idasanutlin. Patients with clinically significant electrolyte abnormalities as per exclusion criteria (Section 5.2) will not be allowed to start idasanutlin treatment. Treatment for correction of above electrolyte imbalances is permitted during screening to meet eligibility. On treatment, electrolytes need to be frequently monitored and any eventual imbalances promptly corrected as per local medical guidelines.

The management of toxicity not listed in Table 7 or Table 8 will be managed as described in Table 6.

8.4 TREATMENT OF OVERDOSE

Study treatment overdose is the accidental or intentional use of the drug in an amount higher than the dose being studied. An overdose or incorrect administration of study treatment is not an adverse event unless it results in untoward medical effects (see Appendix 11 for further details).

Decisions regarding dose-interruptions or modifications will be made by the Investigator in consultation with the Medical Monitor based on the clinical evaluation of the patient.

8.5 PHARMACOKINETICS

Mandatory blood samples will be obtained for patients at the timepoints specified in the SoA (Section 1.2) for determination of plasma concentration of idasanutlin and M4 metabolite. Samples will be reserved for potential analysis of other metabolites. Additional unscheduled PK samples may be obtained if additional PK information is required to better characterize safety and PK profile (e.g., for safety observations, dosing delays, etc.). The date and time of each sample collection will be recorded in the eCRF. Idasanutlin levels will be analyzed by using validated assays.

Details on sampling procedures, sample storage and shipment are given in the lab manual. PK samples will be destroyed no later than five years after the final clinical study report.

Allowed PK sampling assessment windows are as follows:

- Pre-dose assessments: within 2 hours
- Assessments < 2 hours: ± 5 minutes
- Assessments 2–24 hours: $\pm 5\%$ (equal to 3 mins/hr)
- Assessments > 24 hours: ± 2 hours

8.6 PHARMACODYNAMICS

Samples will be collected for pharmacodynamic assessments at the times specified in the SoA (Section 1.2). These samples will be tested for protein, nucleic acid, or other biomarkers relating to the proposed mechanism of action of idasanutlin in PV or other disease-related markers or the improvement of diagnostic assays.

These include, but are not limited to, the molecular status of JAK2 (including V617F or exon 12 mutational status) and TP53 mutational analysis in samples.

Further, gene expression changes may be assessed, including p53 regulated genes may be assessed.

Protein expression may be additionally analyzed for predictive and/or prognostic association with patients benefitting from idasanutlin treatment.

Measurement of cytokines, inclusive of inflammatory cytokine signatures may also be utilized in this study (Pourcelot et al. 2014). These cytokine levels may then be compared to symptom data as generated by the MPN-SAF TSS.

The specimens may also be used for research purposes to identify biomarkers useful for predicting and monitoring response to idasanutlin treatment, identifying biomarkers useful for predicting and monitoring idasanutlin safety, assessing pharmacodynamics effects of idasanutlin treatment, and investigating mechanism of therapy resistance.

Additional markers may be measured in case a strong scientific rationale for these analyses develops. Based on continuous analysis of the data in other MDM2-antagonist studies and this study any sample timepoint or type may be stopped at any time if the data does not support a strong scientific justification to continue.

Whole blood samples will be collected for:

- **Exploratory Biomarker Pharmacodynamic** samples may be acquired before and after treatment to enable assessment of protein or other cellular markers of PV and markers related to the mechanism of action.
- **TBNK Panel Flow Cytometry Blood** for T- and B-cell quantitation by flow cytometry.

Plasma samples will be collected for:

- **Cytokine Assay** as measured utilizing a protein assay.

Serum samples for pharmacodynamic analyses will be obtained for patients as described in SoA (Section 1.2) for:

- **MIC-1** increase to be associated with steady-state exposure of idasanutlin as confirmation of intended mechanism of action engagement.

The following bone marrow samples will be collected:

- **Bone marrow biopsy** for histological assessment of cellularity (age-adjusted normocellularity), morphology on Hematoxylin and Eosin (H & E), blast percentage, and reticulin fibrosis grade. If screening bone marrow biopsy is unsuccessful, a biopsy within 3 months of first dose is required to establish baseline histology.
- **Bone marrow aspirate** for cytogenetics by local routine karyotypic analysis. If bone marrow aspirate sample insufficient/inconclusive, backup whole blood sample for cytogenetics should be used.

Details on sampling procedures, sample storage and shipment are given in the Sample Handling Manual.

Allowed pharmacodynamic sampling assessment windows are as follows:

- Pre-dose assessments: within 2 hours
- Assessments < 2 hours: ± 5 minutes
- Assessments 2–24 hours: $\pm 5\%$ (equal to 3 mins/hr)
- Assessments > 24 hours: ± 2 hours

Pharmacodynamics samples will be destroyed no later than five years after the final CSR. These samples may be used for additional exploratory biomarker profiling, identification, assay development purposes, and assay validation during the development of study or compound-related assays after the mentioned intended uses.

8.7 BIOMARKERS, GENETIC ANALYSIS

8.7.1 DNA Sequencing

Fresh blood for PV-derived DNA and RNA will be collected at baseline for analysis of TP53 and JAK2 mutational status as well as transcript quant for exploratory research on non-inherited biomarkers. Further, DNA and/or RNA extraction will be performed on post-treatment specimens for exploratory research on changes in non-inherited biomarkers (including, but not limited to, cancer-related genes and biomarkers associated with common molecular pathways, or immune-related markers, and also tumor mutation burden).

The following samples will be collected for genetic analysis:

- **Nucleic acid Whole Blood** analysis to include, but are not limited to JAK2 and p53 mutation status (gene sequencing)
- **Paxgene Whole Blood** analysis to include, but not limited to mRNA level of gene expression of various genes.
- **Cytogenetics Whole Blood** for cytogenetics by local routine karyotyping if bone marrow aspirate sample insufficient/inconclusive.

Details on processes for collection and shipment of these samples can be found in the Sample Handling Manual.

Whole blood samples and residual DNA and RNA from these will be destroyed no later than five years after the final CSR. These samples may be used for additional exploratory biomarker profiling, identification, assay development purposes, and assay validation during the development of study or compound-related assays after the mentioned intended uses.

8.7.2 Samples for Research Biosample Repository

Overview of the Research Biosample Repository

The Roche Research Biosample Repository (RBR) is a centrally administered group of facilities for the long-term storage of human biologic specimens, including body fluids, solid tissues, and derivatives thereof (e.g., DNA, RNA, proteins, peptides). The collection, storage and analysis of these specimens will facilitate the rational design of new pharmaceutical agents and the development of diagnostic tests, which may allow for individualized drug therapy for patients in the future.

Specimens will be collected from patients who give specific consent to participate in this optional RBR. Collected specimens will be used to achieve the following objectives:

- To study the association of biomarkers with efficacy, adverse events, or disease progression.
- To increase knowledge and understanding of disease biology.

- To study treatment response, including drug effects and the processes of drug absorption and disposition.
- To develop biomarker or diagnostic assays and establish the performance characteristics of these assays.

Approval by the Institutional Review Board or Ethics Committee

Sampling for the RBR is contingent upon the review and approval of the exploratory research and the RBR portion of the Informed Consent Form by each site's Institutional Review Board or Ethics Committee (IRB/EC) and, if applicable, an appropriate regulatory body. If a site has not been granted approval for RBR sampling, this section of the protocol will not be applicable at that site.

Sample Collection

IF RBR consent is provided, leftover biomarker samples and any derivatives thereof will be stored in the RBR.

Additionally, the following sample will be collected for identification of dynamic (non-inherited) biomarkers:

- Serum to assess exploratory biomarkers

The following samples will be collected for identification of genetic (inherited) biomarkers:

- Blood for DNA extraction

The samples collected for DNA extraction include, but are not limited to, genomic analysis and may be sent to one or more laboratories for analysis.

Genomics is increasingly informing researcher's understanding of disease pathobiology. WGS provides a comprehensive characterization of the genome and, along with clinical data collected in this study, may increase the opportunity for developing new therapeutic approaches. Data will be analyzed in the context of this study but will also be explored in aggregate with data from other studies. The availability of a larger dataset will assist in identification of important pathways, guiding the development of new targeted agents.

For all samples, dates of consent and specimen collection should be recorded on the associated RBR page of the eCRF. For sampling procedures, storage conditions, and shipment instructions, see the separate Laboratory Manual.

RBR specimens will be stored and used until no longer needed or until they are exhausted. The RBR storage period will be in accordance with the IRB/EC-approved Informed Consent Form and applicable laws (e.g., Health Authority requirements).

The repository specimens will be subject to the confidentiality standards (as described under Confidentiality in [Appendix 7](#)).

